15.6.7. Virology

Genotype

Amino Acid Changes
 
 • A mutation is considered present whenever the encoded amino acid residue differs from the amino acid that would have been encoded by the wild-type (e.g., HXB2, NL43) comparator gene; e.g., Q148K. • If the encoded amino acid is seen as a mixture of wild-type and mutant amino acid, e.g., Q148Q/K, the mutated amino acid is considered present at the codon of interest. • If the encoded amino acid is seen as a mixture of two or more amino acids, which may or may not include wild type, e.g., Q184K/H or Q184K/H/Q, etc., for the purposes of calculating the number of mutated amino acids, only one mutation is considered to be present at the codon of interest.

Representation of Amino Acid Changes

Mutations	Amino acid change
T69S	Single mutation from amino acid 'T' (vendor reference) to 'S' (sample) at codon '69'
Q148H/K/R	Mixture of amino acid mutations 'H', 'K' and 'R' (sample) from amino acid 'Q' (vendor reference) at codon '148'
_69_1T	First insertion of amino acid 'T' (sample) at codon '69'
_69_2S	Second insertion of amino acid 'S' (sample) at codon '69'
_69_3S/A	Third insertion of a mixture of amino acids 'S' and 'A' (sample) at codon '69'
L74L/-	Mixture of amino acid 'L' (sample) and a deletion at codon '74'
V75-	Single deletion of amino acid (sample) at codon '75'

Resistance Associated Mutations

- Known INI mutations associated with the development of resistance to BIC, RAL, EVG or DTG:

Amino Acids in HIV Integrase for Analysis	H51Y, T66A/I/K , E92Q/V/G , Q95K, T97A, G118R, F121Y , E138A/K/T, G140A/C/R/S**, Y143C/H/R/K/S/G/A , P145S , Q146P , S147G , Q148H/K/R/N , V151I/L/A , S153F/Y, N155H/S/T , E157Q, G163R/K, S230R, R263K, L68V/I*, L74I/M*, E138D*, V151I*, G193E*
---	--

NOTES:

- Draft listing; may be modified in case of additional substantive data availability.
 - INI mutations listed taken from Stanford HIV Resistance Database (http://hivdb.stanford.edu/DR/cgi-bin/rules_scores_hivdb.cgi?class=INI cited 18Jul2018) and accessed on 06Oct2018.
 - Each INI mutation listed had a score of ≥ 15 . INI substitutions listed above in bold had a score of =60.
- * Denotes additional INI mutations added as they were identified during in vitro passage of DTG or seen in a previous DTG study in INI-experienced participants (ING112574).
- **G140R is potentially associated with CAB based on in-stream data monitoring of CVF participants.

- Major resistance mutations to other classes (i.e., NRTI, NNRTI, PI) as defined by the International Antiviral Society-USA (IAS-USA). The most up to date IAS-USA guidelines available at the time of DBF will be used in the analysis [Wensing AM et al 2017].

Class	Mutations
NRTIs	M41L, A62V, K65R/E/N, D67N, 69 insert, K70E/R, L74V, V75I, F77L, Y115F, F116Y, Q151M, M184V/I, L210W, T215Y/F, K219Q/E
NNRTIs	L100I, K101E/P, K103N/S, V106A/M, V108I, E138A/G/K/Q/R, V179L, Y181C/I/V, Y188C/L/H, G190S/A, H221Y, P225H, F227C, M230I/L,
PIs	D30N, V32I, M46I/L, I47A/V, G48V, I50V/L, I54M/L, Q58E, T74P, L76V, V82A/T/F/L/S, N83D, I84V, N88S, L90M

Note: List generated from IAS_USA Guideline, [Wensing et al. 2017]

Phenotype**Phenotypic Susceptibility**

Phenotypic susceptibility to all licensed antiretroviral drugs and CAB will be determined using PhenoSense HIV assays from Monogram Inc. and will be reported as fold change (FC) in IC50 relative to wild-type control virus NL4-3, i.e., FC of sample virus = IC50 of sample virus/IC50 of control virus.

Phenotypic susceptibilities will be categorised according to FC as shown in tables below (based on Monogram PhenoSense assay). Clinical cutoffs (where available) or biological cutoffs by PhenoSense will be used to define the phenotypic susceptibility of background treatment by Monogram.

Replication capacity is generated as part of standard phenotypic assays.

PhenoSense Algorithm

Drug	Abbreviation	Class	PhenoSense cutoff
Abacavir	ABC	NRTI	(4.5 – 6.5) ^a
Lamivudine	3TC	NRTI	3.5 ^a
Didanosine	ddl	NRTI	(1.3 – 2.2) ^a
Stavudine	d4T	NRTI	1.7 ^a
Zidovudine	AZT (ZDV)	NRTI	1.9
Emtricitabine	FTC	NRTI	3.5
Tenofovir	TDF (TAF)	NRTI	(1.4 – 4) ^a
Delavirdine	DLV	NNRTI	6.2
Efavirenz	EFV	NNRTI	3
Nevirapine	NVP	NNRTI	4.5
Etravirine	ETR	NNRTI	(2.9-10) ^a
Rilpivirine	RPV	NNRTI	2.0
Fosamprenavir/r	FPV/r	PI	(4-11) ^a
Atazanavir	ATV	PI	2.2 ^a
Atazanavir/r	ATV/r	PI	5.2 ^a
Indinavir/r	IDV/r	PI	10 ^a
Lopinavir/r	LPV/r	PI	(9 – 55) ^a
Nelfinavir	NFV	PI	3.6
Saquinavir/r	SQV/r	PI	(2.3 – 12) ^a
Tipranavir/r	TPV/r	PI	(2 – 8) ^a
Darunavir/r	DRV/r	PI	(10 – 90) ^a
Ritonavir	RTV	PI	2.5
Enfuvirtide	T20	FI	6.48
Cabotegravir	CAB	INI	2.5
Raltegravir	RAL	INI	1.5
Elvitegravir	EVG	INI	2.5
Dolutegravir	DTG	INI	(4-13) ^a
Bictegravir	BIC	INI	(2.5- 10)

a. clinical cutoff (lower cutoff – higher cutoff).

Phenotypic Susceptibility

Phenotypic susceptibility to each drug in a participant's background regimen is determined by applying drug-associated cutoffs as defined by the PhenoSense algorithm to the phenotypic fold resistance as below:

Full Sensitivity

Fold Change	Interpretation
> clinical lower cutoff or biological cutoff	resistant
≤ clinical lower cutoff or biological cutoff	sensitive

Partial Sensitivity

Fold Change	Interpretation
> clinical higher cutoff	resistant
≤ clinical higher cutoff and > clinical lower cutoff	partially sensitive
≤ clinical lower cutoff	sensitive

PHENOTYP dataset from Monogram contains the phenotypic susceptibility for each drug derived from the cutoff listed above. Thus, phenotypic susceptibility (i.e. full sensitivity and partial sensitivity) will not be re-derived for our analysis.

Genotypic and Net Assessment Susceptibility

Genotypic and Net assessment susceptibility to all licensed antiretroviral drugs and CAB will be determined from Monogram Inc. Net assessment susceptibility will be reported with the categories of 'resistant', 'partially sensitive', and 'sensitive' as what will be performed for phenotypic susceptibility. Genotypic susceptibility will be reported with the categories of 'resistant', 'resistance possible' and 'sensitive'. Genotypic and Net assessment susceptibility will be assessed at time of CVF using plasma sample, Genotypic susceptibility may be assessed at baseline using PBMC.

15.7. Appendix 7: Reporting Standards for Missing Data

15.7.1. Premature Withdrawals

Element	Reporting Detail
General	
 ● Participant study completion (i.e. as specified in the protocol) was defined as 
 ○ Randomly assigned to either treatment group, completed the randomized Maintenance Phase including Week 100 and did not enter the Extension Phase; ○ Randomly assigned to either treatment group, completed the randomized Maintenance Phase including Week 100, and entered and completed the Extension Phase (defined as remaining on study until commercial supplies of CAB LA + RPV LA Q4W or Q8W regimen become locally available or development of CAB LA + RPV LA is terminated). 
Participants who withdraw from CAB LA + RPV LA and go into the LTFU Phase, and participants who withdraw from oral lead-in will be considered to have prematurely withdrawn from the study treatment.
 
In addition to the 52-week Follow-Up phase required for participants who receive one or more injections with CAB LA or RPV LA, an in-clinic Follow-Up visit will be conducted approximately 4 weeks after the last dose of study medication for participants who withdraw during the oral lead-in period with ongoing AEs, and serious adverse events (SAEs) and also any laboratory abnormalities that are considered to be AEs or potentially harmful to the participant, at the last on-study visit. Assessments at the Follow-up visit should reflect any ongoing complaints (e.g., blood draws to follow a laboratory abnormality). Follow-Up visits are not required for successful completion of the study.
 
 ● Withdrawn participants were not replaced in the study. ● All available data from participants who were withdrawn from the study will be listed and all available planned data will be included in summary tables and figures, unless otherwise specified. ● Withdrawal visits will be slotted as per Appendix 3: Assessment Windows or will be summarised as withdrawal visits.

15.7.2. Handling of Missing Data

Element	Reporting Detail
General	
 ● Missing data occurs when any requested data is not provided, leading to blank fields on the collection instrument: 
 ○ These data will be indicated by the use of a “blank” in participant listing displays. Unless all data for a specific visit are missing in which case the data is excluded from the table. ○ Answers such as “Not applicable” and “Not evaluable” are not considered to be missing data and should be displayed as such.
Outliers	
 ● Any participants excluded from the summaries and/or statistical analyses will be documented along with the reason for exclusion in the clinical study report.

15.7.2.1. Handling of Missing and Partial Dates

Element	Reporting Detail
General	
 • Partial dates will be displayed as captured in participant listing displays.
Adverse Events	
 • The eCRF allows for the possibility of partial dates (i.e., only month and year) to be recorded for AE start and end dates; that is, the day of the month may be missing. In such a case, the following conventions will be applied for calculating the time to onset and the duration of the event: 
 ○ Missing Start Day: First of the month will be used unless this is before the start date of study treatment; in this case the study treatment start date will be used and hence the event is considered On-treatment as per Appendix 4: Study Phases and Treatment State. ○ Missing Stop Day: Last day of the month will be used, unless this is after the stop date of study treatment; in this case the study treatment stop date will be used. • Completely missing start or end dates will remain missing, with no imputation applied. Consequently, time to onset and duration of such events will be missing.
ART/Non-ART Medications or Medical History	
 • Partial dates recorded in the eCRF will be imputed using the following convention: 
 ○ If the partial date is a start date, a '01' will be used for the day and 'Jan' will be used for the month. ○ If the partial date is a stop date, a '28/29/30/31' will be used for the day (dependent on the month and year) and 'Dec' will be used for the month. If medications recorded in the eCRF as prior (e.g. recorded in prior ART or prior ATLAS ART forms, taken prior to study), the earlier date of the imputed and the day prior to the maintenance phase treatment start date will be used, i.e. min (imputed stop date, maintenance phase treatment start date - 1). • For medications with completely missing start date, they will be considered started prior to the maintenance phase treatment start date. • For medications with completely missing stop date, they will be considered ongoing unless recorded in eCRF as prior (e.g. recorded in prior ART or prior ATLAS ART forms, taken prior to study). • For ART booster medications, the start and stop dates are not recorded in the database (i.e. missing), the dates will be imputed to be the same as the dates of their parent medications. • The recorded partial or missing date will be displayed in listings.
Health outcomes	
 • For the health outcomes questionnaire data, please refer to Section 12. • For the summary of individual item scores outputs, missing scores will not be computed.

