15.4.2.1. Treatment States for AE Data

For adverse events, partial AE start date will use imputation as described in Section 15.7.2.1. In the case of a completely missing start date, the event will be considered to have started On-treatment in the Maintenance phase unless an end date for the AE is provided which is before start of study treatment at Maintenance phase; in such a case the AE is assigned as Pre-treatment.

Additional variables will be derived as shown in Table 17.

Table 17 Days since First Dose of Each Study Phase, Days since Phase Start, AE Duration and Relation to Study Treatment

	Definition
Days since First Dose (Days) ^a	AE Start Date – Maintenance Treatment Start Date + 1
Days since Last Dose (Days) ^a	AE Start Date – Date of Last Dose of Study Treatment prior to/on the Start Date of AE + 1
Days since Phase Start	
For AEs in Maintenance Phase: AE Start Date - Maintenance Treatment Start Date + 1
 
For AEs in Extension Phase: AE Start Date – Date of Nominal Week 100 Visit + 1
 
For AEs in Long-term Follow-up Phase: AE Start Date – Date of Last Dose of Study Treatment^b

Duration (Days)	AE Resolution Date – AE Start Date + 1
Drug-related	If relationship is marked 'YES' on Inform/eCRF or value is missing.

NOTES:

- Days since First/Last Dose will only be derived for AEs assigned to maintenance phase, extension phase and long-term follow-up phase.
- Date of Last Dose of Study Treatment = max (Last IM Injection Date, Last Oral Bridging End Date), only applicable to participants who permanently discontinued study treatment.

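### Partial adverse-event dates: the stop day is capped at an undefined treatment stop date with no floor at onset, and the start-day rule can move a pre-treatment event to Day 1

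*SAP*

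**What the plan says.** SAP 15.7.2.1 allows for AE dates recorded with month and year only, and gives the purpose of its rules: "the following conventions will be applied for calculating the time to onset and the duration of the event".

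- **Stop day not recorded:** "Last day of the month will be used, unless this is after the stop date of study treatment". Where the month end falls later than that date, the rule substitutes the date itself: "in this case the study treatment stop date will be used".
- **Start day not recorded:** "First of the month will be used unless this is before the start date of study treatment". Where the first of the month is earlier, the rule moves onset to Day 1 and settles the treatment state with it: "in this case the study treatment start date will be used and hence the event is considered On-treatment".

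SAP 15.4.2.1 carries the start rule into the assignment of treatment state: "partial AE start date will use imputation as described in Section 15.7.2.1". Table 17 in that section defines duration as "AE Resolution Date – AE Start Date + 1".

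Section 15.7.2.1 does not define the treatment stop date. The nearest definition is the note to Table 17: "Date of Last Dose of Study Treatment = max (Last IM Injection Date, Last Oral Bridging End Date"), which applies only to participants who permanently discontinued. Section 15.6.1 treats the same quantity as the end of investigational product when it derives the long-term follow-up study day. Table 15 starts the long-term follow-up phase on the day after it. Table 16, however, counts 35 days (Q4W) or 63 days (Q8W) after the last injection as on-treatment, or one day after the last oral dose if that is later.

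For a completely missing start date, 15.4.2.1 uses the end date: an event known to have ended before treatment began is classed as pre-treatment. The partial-date rule has no such check.

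**The concern.** Capping an unknown stop day at the end of treatment is a convention from daily oral dosing. In this trial participants are followed for AEs well after the last injection, and part of that time counts as on-treatment. A cap at or near the last dose, without a floor at onset, can therefore place resolution before onset.

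The start rule has the opposite weakness. It pulls any earlier partial start forward to Day 1, even when the recorded month or a known end date shows that the event came before treatment. The plan thus handles a completely missing start date more carefully than a partly known one.

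At stake are the displays that use AE duration, such as the injection-site-reaction onset, duration and severity plots (Figures 3.3 to 3.5 in 15.14.5.5), and the treatment state of a few pre-dose serious events.

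**Working it through.** The SAP gives no figure on this point, so there is nothing to reproduce. The rules were applied as written to assumed dates.

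**Stop rule, general result.** Let C be the treatment stop date and S the onset, with S later than C. The recorded stop month cannot precede the onset month, so its last day is on or after S and hence after C. The cap then always applies, and duration = C - S + 1, which is at most 0. If C is the later of last injection and last oral bridging end, Table 15 makes every long-term follow-up AE meet this condition. Each one with a missing stop day therefore gets a duration of zero or less.

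**Stop rule, examples.** Last injection 5 March 2019, no oral bridging. The alternative caps are 9 April (+35 days) and 7 May (+63 days). Possible true durations run from the earliest to the latest stop day that the recorded month and the onset allow.

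| Onset | Stop recorded | Cap at last dose | Cap at +35 | Cap at +63 | Possible true duration |
|---|---|---|---|---|---|
| 6 March | March | 5 - 6 + 1 = 0 | 26 | 26 | 1 to 26 |
| 20 March | March | 5 - 20 + 1 = -14 | 12 | 12 | 1 to 12 |
| 20 April | May | -46 + 1 = -45 | -11 + 1 = -10 | 17 + 1 = 18 | 12 to 42 |
| 10 September | September | -189 + 1 = -188 | -154 + 1 = -153 | -126 + 1 = -125 | 1 to 21 |
| 20 February | April | 13 + 1 = 14 | 48 + 1 = 49 | 69 + 1 = 70 | 41 to 70 |

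Rows 1 and 2 depend on the last-dose reading: with either wider cap they become valid. Row 4, a follow-up event, is negative under all three readings. Row 5 shows truncation: under the last-dose reading, 14 days are assigned where at least 41 must have passed.

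**Start rule, examples.** Treatment start 20 March 2018.

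- Start recorded as February 2018, known end 25 February. The first of the month precedes treatment, so the start becomes 20 March and the event is on-treatment. The end is 23 days before the imputed start, so duration = -23 + 1 = -22.
- Start recorded as March 2018, known end 15 March. The start becomes 20 March, on-treatment. Duration = 15 - 20 + 1 = -4.

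Had the start dates been completely missing, 15.4.2.1 would have classed both events as pre-treatment on the same end dates.

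**The case against.** **The cap is not stated to be the last injection.** This stands. The term is undefined in 15.7.2.1, and the nearest definition also includes the oral bridging end. Treatment state (Table 16) and overall exposure (15.6.4) extend cover to 35 or 63 days after the last injection, and on that reading the -14 day example becomes a plausible 12 days. The wider reading reduces the problem but does not remove it, because follow-up events starting after the wider cap still get zero or negative durations.

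**Same-month starts are deliberately conservative.** This also stands. Treating an event with an unknown day in the treatment-start month as on-treatment is a usual safety convention. The defect is confined to earlier months and to events with a known end before treatment.

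**Few records can be affected before dosing.** Agreed. Appendix 2 limits collection before the first dose to serious events related to study participation or to a concomitantly given sponsor product, and 2.3 limits screening to 35 days.

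**The cap is not always wrong.** An event that truly ended before the treatment stop date, in the same month, is placed closer to the truth by the cap. It would be too strong to say that every missing stop day in or after the month of the last injection is mishandled.

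**Arm imbalance.** A reader might infer from the 63-day and 35-day periods that the error falls unevenly on the arms. The SAP does not support that. Under the last-dose reading the same rule applies in both arms. The injection-site-reaction plots are Maintenance Phase displays, and Table 13 ends that phase for AEs at the start of follow-up antiretroviral therapy in participants who do not enter the Extension Phase, not at day 35 or 63. Long-term follow-up is 52 weeks in either arm (2.3). Under the wider reading the caps would differ by arm, but without counts neither the direction nor the size of any imbalance can be given.

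**Conclusion.** The point holds with limited reach. As written, the stop rule lacks a floor at onset and relies on an undefined date. Taking that date as the end of dosing used in Table 17 and 15.6.1, all long-term follow-up AEs with a missing stop day get durations of zero or less, and events that run past it are shortened. Taking it as last injection plus 35 or 63 days, only events starting after that later date get such durations. The start rule can class a pre-dose serious event as on-treatment with a negative duration.

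The number of affected records is unknown. The stop rule needs a participant with a treatment stop date and an AE with a missing stop day, and it changes duration, not incidence, grade or any efficacy result. The start rule can also change treatment state and so add an event to on-treatment counts, but only for the few event types collected before dosing. Listings show partial dates as recorded, so affected records can be traced. A differential effect between arms is not shown. The rules should still be corrected, because they give impossible values by construction and the repair is small.

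**What to change.** **Missing stop day.** Use the last day of the recorded month, capped at death, study exit or data cut-off rather than at treatment stop, and never earlier than onset. The undefined treatment stop date then drops out of the rule.

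**Missing start day.** Substitute the treatment start date only when the recorded month and year equal those of treatment start and the AE end date is not before treatment start. Otherwise keep the first of the month, and class the event as pre-treatment when it ended, or its recorded month falls, before treatment start. This brings partial start dates into line with the 15.4.2.1 rule for completely missing ones.

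**Cost.** About two lines of SAP text in 15.7.2.1 and a small change to the AE derivation program. No new data are needed.

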$253 \leq \text{Study Day} \leq 308$	$253 \leq \text{Study Day} \leq 322$	Week 40
$295 \leq \text{Study Day} \leq 378$	$295 \leq \text{Study Day} \leq 378$	Week 48
$365 \leq \text{Study Day} \leq 420$	$365 \leq \text{Study Day} \leq 434$	Week 56
$421 \leq \text{Study Day} \leq 476$	$421 \leq \text{Study Day} \leq 490$	Week 64
$477 \leq \text{Study Day} \leq 532$	$477 \leq \text{Study Day} \leq 546$	Week 72
$533 \leq \text{Study Day} \leq 588$	$533 \leq \text{Study Day} \leq 602$	Week 80
$589 \leq \text{Study Day} \leq 644$	$589 \leq \text{Study Day} \leq 658$	Week 88
$631 \leq \text{Study Day} \leq 714$	$631 \leq \text{Study Day} \leq 714$	Week 96

NOTES:

- For post-baseline visits (i.e. Week 4 and afterwards), apply Snapshot analysis windows only to viral load data that is on-treatment (per Table 16) within the Maintenance Phase (per Table 14).
- An on-treatment viral load assessment may be assigned to more than one snapshot analysis window, e.g. on-treatment assessment taken on Study Day 300 will be in both Week 40 and Week 48.

a. ± 6 Week window is always used at key analysis timepoints (Week 48 and Week 96). For analysis timepoint of Week 24, if no viral load data in default window, expand to ± 6 Week window, i.e. ($127 \leq \text{Study Day} \leq 210$) in Week 24 IDMC and Week 24 Analyses, and expand upper bound to +6 weeks in all other analyses.

Table 11 Assessment Windows for Summaries of Long-Term Follow Up Phase Data for Participants Who Received At Least One Injection of CAB+RPV and Permanently Discontinued Study Treatment

Analysis Window	Analysis Timepoint	Target Study Day of Window
$1 \leq \text{LTFU Study Day} \leq 63$	LTFU Month 1/WD ^[a]	30
$64 \leq \text{LTFU Study Day} \leq 135$	LTFU Month 3	90
$136 \leq \text{LTFU Study Day} \leq 225$	LTFU Month 6	180
$226 \leq \text{LTFU Study Day} \leq 315$	LTFU Month 9	270
$316 \leq \text{LTFU Study Day} \leq 405$	LTFU Month 12	360
$(30*m - 44) \leq \text{LTFU Study Day} \leq (30*m + 45)$	LTFU Month m m = 15, 18, 21, ...	7*m

NOTES:

- An assessment may be assigned to both LTFU and maintenance/extension phases.

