Maintenance	For participants continuing into Extension Phase: Maintenance Treatment Start Date < Date \leq Date of Nominal Week 100 Visit Note: 2-hour post-dose ECG taken on the Maintenance Treatment Start Date will be included. For participants not continuing into Extension Phase^[a]: Maintenance Treatment Start Date < Date \leq LTFU ART Start Date Note: 2-hour post-dose ECG taken on the Maintenance Treatment Start Date will be included.
Extension	Participants continuing into Extension Phase^[a]: Date of Nominal Week 100 Visit < Date \leq LTFU ART Start Date

- Date = start or assessment date
- [a] If participants have missing LTFU ART start date (i.e. the participants have not started ART in LTFU yet), only the lower bound of the window will be considered in the derivation.

Table 15 Assignment to Long-term Follow-up Phase

Study Phase	Definition
Long-term Follow-up	Date > max (Last IM Injection Date, Last Oral Bridging End Date)

- Date = Assessment/Start Date
- For AEs leading to withdrawal and started on the same date as LTFU ART Start Date, maintenance phase or extension phase depending on participant's continuation status to extension phase, instead of long-term follow-up phase, will be assigned. Refer to [Table 13](#) for details.

Only participants who received at least one CAB and/or RPV injection will enter the long-term follow-up. Note that the long-term follow-up phase and maintenance/extension phases are not necessarily mutually exclusive and are to be defined with separate phase variables in the datasets. For example, an Q4W IM participant who has Week 44 injection and withdrawal at Week 48 without receiving Week 48 injection, the “Week 48 withdrawal visit” belongs to both the maintenance phase and long-term follow-up phase.

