15.6. Appendix 6: Derived and Transformed Data

15.6.1. General

Multiple Measurements at One Time Point
 
 If after window assignment there are multiple valid assessments of a parameter within the same window, refer to Section 15.3.6 for determination of the value to be used for summary statistics of observed values. Assessments not chosen for use in summary statistics will still appear in the associated listings. Assessments not chosen for use in summary statistics by this algorithm will still appear in the associated listings. Also, all applicable valid assessments, irrespective of proximity to the target study day, will be used when categorizing values across visits, such as 'maximum grade' or 'at any time', and for any algorithm that has specific rules for which observation to use (e.g. snapshot algorithm, LOCF or CVF identification).

Treatment Start Date
 
Treatment start date is defined as follows:
 
Maintenance Phase
 
 Date of first ATLAS-2M dose of CAB+RPV (oral or injection) entered onto the IP exposure eCRF form. 
Extension Phase
 
 For participants not continuing into extension phase, treatment start date is missing. For participants continuing into extension phase, treatment start date is the date of first dose of CAB+ RPV (oral or injection) at or after nominal Week 100 visit. 
Long-term Follow-up Phase
 
 If a participant is still on study treatment, or permanently discontinued the study treatment and did not have any previous injections, treatment start date is missing. If a participant permanently discontinued the study treatment and had at least one injection, treatment start date is the date of first ART treatment after the last dose of study treatment (oral or injection).

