
 Last on-treatment VL during Week 48 prior to/on the date of change ≥ 50 c/mL 	HIV-1 RNA ≥ 50	Data in window not below 50

 Last on-treatment VL during Week 48 prior to/on the date of change < 50 c/mL 	HIV-1 RNA < 50	

 No VL during Week 48 prior to/on the date of change 	HIV-1 RNA ≥ 50	Change in background therapy
4. If permitted change ^[a] in background therapy during Week 48 AND the last on-treatment VL prior to/on the date of change is ≥ 50 c/mL (NA to this study)		
4.1 this last on-treatment VL occurs prior to Week 48	HIV-1 RNA ≥ 50	Change in background therapy
4.2 this last on-treatment VL occurs during Week 48 but prior to/on the date of change	HIV-1 RNA ≥ 50	Data in window not below 50
5. If none of the above conditions met		
5.1 On-treatment VL available during Week 48		

 Last on-treatment VL during Week 48 ≥ 50 c/mL 	HIV-1 RNA ≥ 50	Data in window not below 50

 Last on-treatment VL during Week 48 < 50 c/mL 	HIV-1 RNA < 50	
5.2 No on-treatment VL during Week 48		
5.2.1 If participants still on study, i.e. a participant has not permanently discontinued the study treatment yet, or if a participant permanently discontinued the study treatment and the upper bound of analysis snapshot window is prior to the following date: Q8W arm: Min[max(Date of last injection + 63, Date of Last Dose of Oral CAB+RPV + 1), Withdrawal Date] Q4W arm: Min[max(Date of last injection + 35, Date of Last Dose of	No virologic data at Week 48 Window	On study but missing data in window

Oral CAB+RPV + 1), Withdrawal Date] , where 'Withdrawal Date' refers to the date the participant failed to complete per corresponding conclusion form.
		

5.2.2 If participants withdraw before/during Week 48 due to
		

5.2.2.1 Safety reasons (e.g. AE/death, liver chemistry stopping criteria, renal toxicity withdrawal criteria, QTc withdrawal criteria etc, as recorded in eCRF Conclusion form)
	
No virologic data at Week 48 Window
	
Disc due to AE/death

5.2.2.2 Non-safety related reasons (e.g. Lack of efficacy, protocol deviation, withdrew consent, loss to follow-up, study closed/terminated, investigator discretion etc, as recorded in eCRF Conclusion Form)
		

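### A month-only switch-ART start date is set to the 1st of the month, which can close the Maintenance Phase too early and drop a valid withdrawal or Week 48 viral load from Snapshot

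*SAP*

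**What the plan says.** The rule for ART and non-ART medications in SAP Section 15.7.2.1 opens with "Partial dates recorded in the eCRF will be imputed using the following convention" and continues "If the partial date is a start date, a '01' will be used for the day and 'Jan' will be used for the month". The natural reading is that only the missing fields are filled. A date with month and year becomes the 1st of that month, and a date with year alone becomes 1 January. No lower bound follows. In the same section, partial adverse event start dates do have one ("First of the month will be used unless this is before the start date of study treatment"), and imputed stop dates of prior medications are capped.

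Three other rules make the ART start date matter for efficacy:

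- Section 15.6.1 (Treatment Start Date, Long-term Follow-up Phase), for a participant who stopped treatment after at least one injection: "treatment start date is the date of first ART treatment after the last dose of study treatment (oral or injection".
- Section 15.4.1, Table 14, Maintenance Phase for participants not continuing into Extension: "Maintenance Treatment Start Date < Date \leq LTFU ART Start Date". If the LTFU ART start date is missing, "only the lower bound of the window will be considered in the derivation".
- Section 15.3.2, notes to Table 10, for post-baseline visits: "apply Snapshot analysis windows only to viral load data that is on-treatment (per Table 16) within the Maintenance Phase (per Table 14".

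Table 16 counts data as on-treatment up to 35 days (Q4W) or 63 days (Q8W) after the last injection. Within the Long-term Follow-up phase it also ends on-treatment status at the LTFU ART start date.

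**The concern.** The imputed date is the earliest that the recorded month allows, and it serves as the end of a phase. Any error therefore shortens the Maintenance Phase. A viral load taken before the new ART actually began, and within the on-treatment limit of Table 16, is treated as if it came after the switch. Table 16 does not bring it back: a sample after the imputed ART start falls outside Maintenance and is post-treatment within Long-term Follow-up.

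The participants affected are those who stop treatment, whose last viral load often decides the Snapshot category. A viraemic withdrawal result could become missing data, and a suppressed one could stop counting as suppressed. The same date also bounds the adverse event phases (Table 13) and the medication categories (Table 2).

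**Working it through.** **Date logic, two examples (day missing)**

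1. Q4W: last injection 20 February; withdrawal viral load and ART start both 20 March, 28 days later; ART start recorded as March only. The imputed start is 1 March, which is after the last dose and so becomes the LTFU ART start. Maintenance ends on 1 March. The 20 March sample is within 35 days of the injection but is not in Maintenance, so Snapshot ignores it.
2. Q8W: last injection 5 November; viral load and ART start both 31 December, day 56; ART start recorded as December only. The imputed start is 1 December. The sample is inside the 63-day limit but 30 days past the end of Maintenance.

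**How often, given a partial date**

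Assumptions, not in the SAP: the viral load is drawn 56 days (Q8W) or 28 days (Q4W) after the last dose, ART truly starts 0, 7, 14 or 28 days after that, and the last dose takes every date in two calendar years (730 positions). The viral load is lost if last dose < imputed ART start < viral load date.

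| True ART lag | Day missing: lost, Q8W | Day missing: lost, Q4W | Day and month missing: lost, Q8W | Day and month missing: lost, Q4W |
|---|---|---|---|---|
| 0 days | 96.7% | 88.8% | 15.1% | 7.4% |
| 7 days | 73.8% | 73.7% | 15.1% | 7.4% |
| 14 days | 50.8% | 50.7% | 15.1% | 7.4% |
| 28 days | 4.9% | 4.9% | 15.1% | 7.4% |

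Q4W is lower at lag 0 because in 7.9% of positions the 1st of the month falls on or before the last dose. The words after the last dose in Section 15.6.1 then filter the date out, and the viral load is kept.

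The same filter governs year-only dates. 1 January is on or before the last dose in 77.0% to 84.7% of positions (Q8W) and 84.7% to 92.3% (Q4W). The LTFU ART start is then treated as missing, the phase has no upper bound, and the ART appears to have been taken during study treatment.

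**What a lost value does to the endpoint (Section 15.9)**

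- *Non-safety withdrawal, no other value in the window.* The last remaining on-treatment value decides. If it is below 50 c/mL, or there is none, the participant has no virologic data. A failure disappears only if viraemia was first seen at the excluded draw.
- *Excluded value was the in-window result of 50 c/mL or more.* The failure disappears unless a remaining value keeps it.
- *Excluded value was suppressed.* The participant leaves the group below 50 c/mL. The primary count normally does not change. It would rise only if the value then left as last were 50 c/mL or more.

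**Size of one reclassification**

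The SAP gives 510 per arm and a 4% margin. One participant is 1/510 = 0.196 points. The upper bound uses the Sato variance of Section 7.1.5.1, applied without strata, with n = m = 510, N = 1020 and W = nm/N = 255:

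var = (dP + Q)/W², where P = [n²y − m²x + nm(m − n)/2]/N² and Q = [x(m − y) + y(n − x)]/(2N).

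Illustrative counts, 10 failures on Q4W:

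- x = 19: d = 0.017647; P = −9/4 = −2.25; Q = (9500 + 4910)/2040 = 7.0637; var = (−0.0397 + 7.0637)/65025 = 0.00010802; upper bound = 1.765 + 1.96 × 1.0393 = 3.80%.
- x = 20: d = 0.019608; P = −2.5; Q = (10000 + 4900)/2040 = 7.3039; var = (−0.0490 + 7.3039)/65025 = 0.00011157; upper bound = 1.961 + 1.96 × 1.0563 = 4.03%.

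One participant moves the bound by 0.23 points here, and by about 0.23 to 0.25 points over similar counts.

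**The case against.** The case against is substantial.

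- **The effect needs several things together:** a participant who stopped treatment, a partial switch-ART date, and a viral load between the imputed and true dates. Nothing in the SAP shows that any such date exists. This stands, and every percentage above is conditional on one.
- **Most losses leave the primary count alone.** A lost suppressed value normally matters only for the endpoint below 50 c/mL, whose margin is 10%. A participant withdrawn after confirmed failure normally keeps the earlier viraemic value and still counts as 50 c/mL or more. This also stands.
- **There are partial safeguards.** The SAP lists partial dates as recorded, has a listing of ART received in long-term follow-up, and requires database cleaning before the analysis. These could reveal a problem but do not change the derivation.

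Two stronger readings are tempting, and the SAP does not support them. A reader might infer that 1 January dates generally remove the viral load. They mostly do not, because the last-dose filter intervenes and Table 16 still caps on-treatment data. A reader might also infer that the misdated ART triggers the Snapshot rule on changed therapy, where "No VL during Week 48 prior to/on the date of change" leads to 50 c/mL or more. That rule concerns non-permitted changes in therapy. ART after stopping injections is the planned follow-up step (Section 2.3), and no section classes it as such a change.

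**Conclusion.** The point holds for month-only dates. Four stated rules together exclude a viral load that was on-treatment and drawn before the new ART began. Given such a date and prompt ART, the loss is usual: 96.7% (Q8W) or 88.8% (Q4W) when ART starts on the visit day, falling to 5% at a 28-day lag. For year-only dates the main fault is different: the ART is misplaced into the study-treatment period, and the viral load is lost through Table 14 in only about 15% (Q8W) or 7% (Q4W).

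The expected effect on the primary result is small and its direction mixed. It would matter only near the margin, where one participant can move the bound from 3.80% to 4.03%. These figures rest on the assumed visit timing, the illustrative counts and an unstratified calculation. The number of partial dates is unknown.

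**What to change.** Add one rule to Section 15.7.2.1. For ART recorded as started after study treatment was stopped, set a partial start date to the latest of:

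- (a) the first date that the recorded fields allow;
- (b) the day after the last study dose;
- (c) the date of the last on-study visit or viral load before LTFU ART (withdrawal or LTFU Month 1 visit), if it falls in the recorded month or year.

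Element (c) is essential. With (a) and (b) alone, 96.7% of viral loads are still lost in both arms when the day is missing and ART starts on the visit day; in the Q4W example the later of 1 March and 21 February is still 1 March. With (c), the same enumeration loses none. Naming the LTFU Month 1 visit matters because, under protocol amendment 1, participants who had received an injection did not have a withdrawal visit (notes to Table 11).

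Also list every imputed ART date that sets a phase boundary.

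The cost is one added rule, a small derivation change and one listing. The downside is that some viral loads drawn shortly after ART really began may be kept; the listing would show them for review before database freeze.
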